### 1. Abstract

- a. Provide no more than a one page research abstract briefly stating the problem, the research hypothesis, and the importance of the research.

The overall goal of the study is to counter the effects of increased N-methyl-D-aspartate (NMDA)/glutamate receptors in MeCP2-mutation-positive Rett syndrome (RTT) subjects by use of a placebo-controlled trial of dextromethorphan (DM), an agent known to block the NMDA receptor channels. The drug dose of DM will be 5mg/kg/day as this dose showed optimal results in our previous dose-effect study. We anticipate improved cognition and temperament, and reduced seizure frequency.

RTT is a neurodevelopmental disorder with devastating consequences to both brain and systemic neurons. Despite a prominent 50% reduction in the number of synapses, postmortem brain autoradiographic studies demonstrate a striking and disproportionate increase in the number of glutamate/NMDA (N-methyl-D-aspartate) subtype of receptors in the prefrontal cortex, especially in younger patients. DM blocks NMDA receptor channels, which improve some clinical manifestations of RTT (eg, cognitive and behavioral deficits, seizures) by reducing the excitotoxic damage and preventing the degree of intellectual disability over the long term. Presently, there is no effective therapy or definitive treatment for RTT, other than palliative care, therefore, our overall specific aim in this biologically-based study is to test the efficacy of DM vs placebo in RTT to block the disproportionate numbers of glutamate/NMDA receptors in the brain and alleviate symptoms. This study holds promise for improved quality of life for girls with RTT, by helping to reduce the degree of functional impairment in this population. Moreover, this study would lend itself to a mode of therapy for other epileptic conditions also associated with glutamatergic excitotoxicity.

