## 7. **Study Statistics**

- a. Primary outcome variable. Improvement in cognition.
- b. Secondary outcome variables. Improvement in behavior.  
*Exploratory outcome variables:* Reduced seizure frequency; improvement in the Quality of Life and Rett Syndrome Behavior questionnaires.
- c. Statistical plan including sample size justification and interim data analysis.

The data will be analyzed when all 60 participants (30 subjects in the placebo group and 30 subjects in the DM group) have completed the 3-month the trial.

Neuropsychological measures for Mullen and VABS: Subjects will be assigned to intervention in a randomized manner as described in randomization. The neuropsychological measures to establish relative cognitive and adaptive competence of the 2 groups to be comparable, age equivalent scores on the Mullen and VABS measures will be compared between groups using 2x2 repeated measures analysis of variance (ANOVA) with the between subjects factor being drug or placebo and within subjects factor being time. Changes in cognitive measures (Mullen and VABS) will be correlated with the behavior measures and seizure frequency.

We based our sample size on the primary outcome, which are the receptive language age equivalent scores on the Mullen scale. There is no established minimal important difference for the Mullen score that is widely accepted and would provide a reasonable effect estimate for sample size calculation. However, a distribution-based estimate of the minimal important difference can be derived from the standard errors of measurement (SEM) that have been

Date: April 12, 2013

Principal Investigator: [name]

Application Number: NA\_00064949

reported for the Mullen subscales (chapter 6 of the Mullen scale) and 1 SEM provides an accepted approximation of the minimal important difference. To detect a 4 point difference (1 SEM) in the receptive language age equivalent scores on the Mullen scale between the groups and assuming a standard deviation of 5 points (based on our pilot data) we need a total sample size (both groups) of 50 patients at a significance level of 0.05 (two-sided) and a power of 80%. Assuming a dropout rate of around 15% the required sample size increases to 60 patients.

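### The planned correlations of cognitive change with behavior and seizure measures name no treatment arm; one coefficient over all children would mix a shared drug effect with a child-level association

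*Combined protocol and SAP*

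**What the plan says.** Section 7c compares Mullen and VABS age equivalents between groups by a 2x2 repeated measures ANOVA, "with the between subjects factor being drug or placebo and within subjects factor being time". The next sentence is the only one on the correlation analysis: "Changes in cognitive measures (Mullen and VABS) will be correlated with the behavior measures and seizure frequency". It does not say whether the arms are combined, kept apart or adjusted for. It also names no coefficient or test and does not say what conclusion will be drawn. No other section fills these gaps.

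The Abstract expects the drug to act on several outcomes at once: "We anticipate improved cognition and temperament, and reduced seizure frequency". Effect size and spread are given for one outcome only, Mullen receptive language: "To detect a 4 point difference (1 SEM) in the receptive language age equivalent scores on the Mullen scale", "assuming a standard deviation of 5 points (based on our pilot data". Behavior is secondary, and seizure frequency is exploratory.

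**The concern.** The usual way to carry out an unqualified instruction to correlate two variables in a trial is to compute one coefficient over everyone. In a two-arm trial that coefficient has two sources. One is the association between the outcomes among children on the same treatment. The other is the separation of the arm means. If DM raises cognition and also improves behavior, treated children tend to be higher on both and placebo children lower on both. The pooled data then show a correlation even when the outcomes are unrelated within each arm.

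At stake is the interpretation. A pooled coefficient is easily taken to mean that the children who gained cognitively were those whose behavior or seizures improved. If the drug works as the Abstract hopes, part or all of that coefficient could simply restate that the drug affected both outcomes.

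**Working it through.** **Inputs from the documents (Section 7c)**
- Difference of 4 points and SD of 5 points on Mullen receptive language: d1 = 4/5 = 0.8.
- Equal allocation: "30 subjects in the placebo group and 30 subjects in the DM group".
- Evaluable total: "we need a total sample size (both groups) of 50 patients"; 60 after allowing for about 15% dropout.
- Design "at a significance level of 0.05 (two-sided) and a power of 80"%. The two-sided 0.05 level is carried over to the correlation test, for which the plan states none.

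**Assumptions, not in the documents**
- Drug effect on the second outcome, d2, in SD units of its change and in the direction of improvement: 0, 0.3, 0.5 or 0.8.
- The SD of 5 is the SD of change.
- Zero correlation within arm, and normal change scores.

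**1. The plan's own figure.** n per arm = 2 × (1.96 + 0.84)² × (5/4)² = 24.5, so 25 per arm and 50 in total, as stated. The t-based version gives 26 per arm. With dropout, 50/0.85 = 58.8, so 59 against the stated 60. The sample size reproduces, so d1 = 0.8 is a fair reading of the planned effect.

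**2. Induced correlation.** With equal arms, a shift of d adds d²/4 to a unit within-arm variance, and the two shifts add d1·d2/4 to the covariance. Hence

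r = (d1·d2/4) / √[(1 + d1²/4)(1 + d2²/4)]

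With d1 = 0.8, 1 + d1²/4 = 1.16:
- d2 = 0: r = 0
- d2 = 0.3: 0.06/√(1.16 × 1.0225) = 0.055
- d2 = 0.5: 0.10/√(1.16 × 1.0625) = 0.090
- d2 = 0.8: 0.16/1.16 = 0.138

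**3. Chance of p<0.05 when nothing is correlated within arm.** Simulation, 40,000 runs per case, Pearson test:

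| d2 | Induced r | Pooled, N = 50 | Pooled, N = 60 | Arm-adjusted, N = 50 / 60 |
|---|---|---|---|---|
| 0 | 0 | 4.8% | 4.8% | 4.8% / 4.8% |
| 0.3 | 0.06 | 6.7% | 6.9% | 5.4% / 5.1% |
| 0.5 | 0.09 | 9.3% | 10.5% | 5.0% / 5.1% |
| 0.8 | 0.14 | 15.9% | 18.7% | 5.1% / 5.1% |

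The Fisher z approximation gives 15.8% for the last row at N = 50, in agreement. The last column subtracts each arm's mean from both variables and tests on N − 3 degrees of freedom. The mean correlation is then 0.00.

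**4. Sensitivity to the meaning of the SD.** Section 7c does not say whether 5 points is the SD of the score or of its change. If it is the SD of the score, the SD of change is 5√[2(1 − ρ)] for a pre-post correlation ρ. For assumed ρ of 0.3, 0.5, 0.7 and 0.8, d1 is 0.68, 0.80, 1.03 and 1.26. With an equally large effect on the second outcome, the induced r is 0.10, 0.14, 0.21 and 0.29.

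**The case against.** The strongest reply is that the plan never says the arms will be pooled. The sentence is silent, and it follows directly on an analysis that has treatment as a factor, so correlations by arm or adjusted for arm would also be consistent with it. This stands in part: pooling is inferred from an omission. But nothing in the text prevents it, and a single coefficient is the plain execution of what is written.

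Four stronger readings are tempting, and the documents do not support them.
- *Any effective drug would create a correlation.* It would not. DM must move both outcomes being correlated; with an effect on cognition alone, r is 0 and the rejection rate stays at about 5%.
- *The plan assumes 0.8 SD on both outcomes.* It plans that effect for Mullen receptive language only. No size is given for any behavior or seizure measure, so 16 to 19% is the top of an assumed range. Larger scenarios, such as 1.2 SD on both outcomes (r = 0.26, rejection about 48 to 56%), have no basis in the stated planning effect.
- *Changes in cognition are set against levels of behavior and seizures.* The sentence attaches the word for change only to the cognitive measures. However, Section 4a says that results will be compared with each child's baseline, and Sections 7a and 7b define the outcomes as improvement or reduction. Change on both sides is the likelier intention. This needs a clarifying word; it is not a separate fault.
- *A false conclusion is built into the plan.* No hypothesis, significance level or interpretation is attached to these correlations. A pooled association is genuine as a description of the whole sample. It misleads only when read as a link between children's individual responses.

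**Conclusion.** The point holds as a correction to a supporting analysis. The correlation sentence leaves arm out. Followed plainly, it would mix a shared drug effect with a child-level association in the situation the Abstract anticipates. The induced correlation is small, at most about 0.14 over the range tried with the SD of 5 taken as the SD of change. The chance of a nominally significant result rises from 5% to between 7% and 19% when the second effect is between 0.3 and 0.8 SD. If DM has no effect, or affects only one of the two outcomes, there is no inflation.

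These figures rest on assumed effects for the second outcome, zero within-arm correlation and normal change scores. Seizure counts are probably skewed, so the percentages are rough for that outcome. The between-group comparison of the primary outcome and the sample size do not depend on this analysis. The change is worth making because it is nearly free, but nothing in the trial's main conclusion turns on it.

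**What to change.** In Section 7c, replace the correlation sentence with one to this effect: partial correlations, adjusted for treatment arm, will be computed between change from baseline in Mullen and in VABS and change from baseline in each behavior measure and in seizure frequency; the correlations will also be shown separately by arm.

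The same edit should name the coefficient and list the behavior measures, because Section 2 places VABS among them while Section 7c treats it as cognitive.

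The cost is one sentence, trivial programming and one degree of freedom for arm (N − 3 instead of N − 2). Adjustment for arm alone restored the error rate to about 5% in every case tried. Adding the two baseline values is optional and would bring the total to three degrees of freedom, which is still minor with 50 to 60 children.

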## 8. Risks

a. Medical risks, listing all procedures, their major and minor risks and expected frequency.

*Dextromethorphan:* Potential major risks include reversible type-1 diabetes, and allergic skin rash. Potential minor risks include lightheadedness, nystagmus, agitation, persistent nausea and/or vomiting, increased liver enzymes, and slurred speech. Dextromethorphan may be associated with mild and infrequent occurrence of dizziness, drowsiness, urinary retention, ataxia, fatigue, and dystonia.

Infrequently, patients on other medications including antipsychotics, lithium, SSRI's, MAO inhibitors may experience psychosis, serotonin syndrome, and hyperthermia. Long-term studies have not been performed with DM, and there may be unknown long-term side effects.

*Blood draw:* The health risk of venipuncture (blood draw) is negligible. There is minimal discomfort from the needle during insertion, with a slight risk of bleeding, bruising, or infection following the blood draw. Subjects may be fearful and have discomfort during the blood draw.

*Blood pressure monitor:* Minimal discomfort may be experienced when the cuff is in place around the child's arm.

*Pregnancy Test and Result:* In post-menarchal subjects (which would be very few given the younger age of this study population), a serum pregnancy test will be performed on the first day of admission. Parents will be informed about the need and rationale (ie, drug effect) for the pregnancy test. If they decline the pregnancy test because of any concerns, they will be unable to participate in this study. If they agree, the risk of learning that their child's test is positive and subsequent removal from the study may cause emotional distress to the parents and family. A positive result will be discussed with the family with the necessary level of sensitivity.

*EKG:* Rarely, there may be a topical skin reaction to the electrode paste or slight discomfort during placement of electrodes.

*Behavioral and Psychological evaluations:* During the intake interviews used to gather information for the questionnaires or scales during these evaluations, parents may choose not to

Date: April 12, 2013

Principal Investigator: [name]

Application Number: NA\_00064949

answer any question(s) that may cause them discomfort, which will be handled empathetically and compassionately.

*Nutrition Assessment:* During the interview with the nutritionist to gather information about the subjects' diet, food preferences, food allergies, etc., some question(s) may cause parents discomfort. Slight discomfort may occur when measuring body mass, head, weight, height.

*Interview Discomfort:* During interviews to obtain information for the intake/clinical questionnaires, the parent(s) may decline to answer any question that may cause them discomfort, which will be handled empathetically and compassionately.

*Risk of Disclosure of Information/Loss of Privacy:* There is a risk of disclosure of information/loss of privacy; however, many steps are taken to minimize this risk as described below.

*Disruption to work or school schedules:* Parents or participants may undergo disruption to their work and/or school schedules when committing the necessary time to undergo the two 3-day inpatient admissions and the two required outpatient interim evaluations during the 3-month drug trial.

b. Steps taken to minimize the risks.

All subjects will be by handled by experienced staff at both Johns Hopkins and the Kennedy Krieger Institute, who are well qualified to handle and address any discomfort or concerns. Subjects are carefully screened and monitored before and after all study procedures. Also, during the interim period between the initial and 3-month follow-up admissions, subject status is assessed by at least weekly telephone calls by the PI, research associate, or research nurse, during the first month, and at least once/month thereafter until the end of this 3-month drug trial. Moreover, interim evaluations performed by us or by subjects' local physicians at 2 weeks and 1 month will identify any abnormality(ies) during the drug trial, and any test showing a deviation from normal will be repeated as a clinically-indicated test that is not paid for by this study.

In addition, the following additional steps will be taken to minimize the risks:

*Dextromethorphan (DM):* Patients on known drugs that could interact with dextromethorphan, including those listed above, are excluded from participating in this study (see Exclusion Criteria). Withholding DM or placebo reverses the symptoms without residual effects. In addition, our research pharmacist provides each participant a *Dextromethorphan Patient Information Sheet*, explains to parents the administration and dosage at discharge when provided with the DM or placebo, and provides a contact phone number if they have any questions about DM.

*Blood draw:* Experienced personnel will draw the blood. Bleeding, bruising, or infection from needle insertion can be readily treated. Our staff is well qualified to address possible fear or discomfort during the blood draw.

*Blood pressure monitor:* Experienced personnel will place the cuff around the arm.

*Pregnancy Precautions:* In those very few post-menarchal subjects, a serum pregnancy test will be performed on the first day of admission; if positive, the subject will be removed from the study.

*EKG:* Any topical skin reaction can be readily treated.

*Behavioral and Psychological evaluations:* Parents are informed prior to the interviews that they can choose not to answer any questions that may make them feel uncomfortable or upset. The psychiatrist and the psychologist are well experienced, empathetic, and compassionate during the interviews.

Date: April 12, 2013

Principal Investigator: [name]

Application Number: NA\_00064949

Nutrition Assessment: During the interview, parents can choose not to answer any question(s) that may make them feel uncomfortable or upset. An experienced nutritionist in the PCRU will perform the body measurements.

Interview discomfort: Parents are informed prior to the interviews that they can choose not to answer any questions that may make them feel uncomfortable or upset. The interviewers are well experienced, empathetic and compassionate during the interviews.

Risk of disclosure of information/loss of privacy: Many steps are taken to prevent the risk of disclosure of information/loss of privacy, such as deidentifying/coding information and samples; storing identifying data separate from deidentified data in locked offices with limited/restricted access; password-protected and access-restricted databases. Release of information is provided only with appropriate signed authorization by parent. The blood samples are for research purposes only, and not for distribution for sale or for selling any products derived from the blood.

Time commitment: We will be as flexible as possible with scheduling the inpatient admissions to accommodate the family's schedule.

c. Plan for reporting unanticipated problems or study deviations.

The DSMB, IRB, KKI's RCO, JHH-ICTR, and the FDA, will be immediately notified of adverse effects by a *Problem/Event Report Form* completed by the PI.

The Data Safety Monitoring Board (DSMB), IRB, KKI's Research Compliance Office, JHH-ICTR, and the FDA, will be immediately notified of protocol events by an *Problem/Event Report Form* completed by the PI.

The DSMB, which is updated every 2 months by the PI with a progress report, will be chaired by [name], Professor, Department of Pediatrics, JHMI and Vice President of KKI Training Program; and will include [name], Asst. Professor of Neurology, JHMI; [name], Professor of Neurology, Johns Hopkins University School of Medicine. They will meet with the PI and Research staff at least annually to discuss progress and adverse events. The DSMB will assess "reasonable safety" and make changes if and when appropriate upon notification of adverse effects by the PI. The DSMB will make recommendations for protocol and/or consent modifications, suspension, or early termination of the trial. The PI will then inform the IRB and FDA of any recommended changes or suggestions. The DSMB will not have contact with patients or families.

d. Legal risks such as the risks that would be associated with breach of confidentiality.

There are very few to no legal risks associated with breach of confidentiality, as all information is shared only between researchers participating in this study, parent(s), and those authorized by them. Information is deidentified when shared with other research collaborators.

e. Financial risks to the participants.

This study has sponsorship from the FDA # 004247-01 and by the JHH-ICTR. Monies are given to the Institute and not to investigators.

Both the initial and follow-up 3-day hospital admissions to the PCRU, the subject's meals, including all proposed test procedures/evaluations performed during those two inpatient admissions as part of the study protocol are paid for by this research study. In addition, the costs of the required two interim maintenance evaluations (ie, neurological eval, EKG, DM levels, CBC, CMP (electrolytes/ LFTs) to be done at 2 weeks and 1 month are paid for by this research study.

Date: April 12, 2013

Principal Investigator: [name]

Application Number: NA\_00064949

If participants live more than 5 hours driving distance from Johns Hopkins, the study will reimburse round trip travel costs (up to \$500 for the subject and up to \$500 for one parent (up to a total of \$1,000 per visit)).

For those driving, reimbursement will be processed after discharge from the study, per Federal reimbursement rate for round trip mileage.

**Not paid for by us:** Any clinical/laboratory assessments required outside of this study's protocol, or those tests to be repeated as clinically-indicated tests.

## 9. Benefits

- a. Description of the probable benefits for the participant and for society.

**Participant:** There are no individual medical benefits for participating in this study.

Dextromethorphan may improve cognition and behavior or lessen or diminish seizures. The measurement of cytokines and glutamate in serum and released from peripheral blood mononuclear cells will determine whether treating children with dextromethorphan modifies the cytokine and glutamate levels, and reflect this process in brain. In addition, since the subject will be evaluated and followed by a multidisciplinary team who will address the associated neurological deficits that occur in RTT, the family will be advised on current treatment(s) available for such impairments, and would be informed in the future should new therapeutic interventions become available. All tests and evaluations as part of the research protocol are performed free of charge by experienced professionals involved in the study.

**Society:** Results of diagnostic test procedures/evaluations may provide understanding of the biological basis of RTT. Understanding the neurobiology of RTT will be valuable to other mental retardation syndromes such as autism and Fragile-X and, thus, help individuals suffering with these disorders as well. We are expected to publish results of this study in the medical literature to be available to the general public, so that larger populations of RTT patients may benefit if favorable results are noted, or avoid DM use in future if no efficacy is proven.

## 10. Payment and Remuneration

- a. Detail compensation for participants including possible total compensation, proposed bonus, and any proposed reductions or penalties for not completing the protocol.

None

